### **Statistical Analyses:**

**EEG:** QUASAR will analyze the EEG data to track changes in alpha activity over the course of the treatment and correlate those to the clinical outcomes. Change in Alpha activity will be calculated between the first and last EEG recordings after the 20 sessions. Furthermore, QUASAR will review the data to determine the minimal subset of electrode locations that would yield reliable detection of alpha activity needed for this NF protocol.

**Behavioral and Cognitive outcomes:** QUASAR will conduct statistical analysis of the results of the pain assessments conducted prior to and after treatment with paired t-test or Wilcoxon signed-rank tests to determine the effects of the treatment (both across the first and last sessions and across the entire 20 sessions). In addition, QUASAR will correlate the clinical outcome measures to the EEG results using cross-correlation analyses and Wilcoxon signed-rank test and will account for multiple comparisons according to the methods described in Mayaud et al, 2019.

**Questionnaires:** Usability survey results will be tabulated and analyzed by QUASAR to inform the design of

the Phase II device.

## **10. HUMAN SUBJECTS**

In order to meet the aims of the study, we will enroll up to 25 subjects that consent and complete all study procedures. Anticipating a standard 10-50% drop-out rate (consented and withdrawn or dropped out), the estimated accrual will be a maximum of 25 total subjects at all sites, depending on screen failures and drop out.

The plan is to recruit subjects UCSD, with a maximum enrollment of 25 subjects.

### **Subject selection:**

Approval from the UCSD IRB will be obtained prior to study enrollment. Informed, written consent will be obtained from ALL subjects who agree to participate. We expect representation of minorities since we will recruit the subjects from the San Diego area, which has good representation from Hispanic, Asian and African American communities. There will not be any exclusion based on race or ethnicity.

### **Inclusion/exclusion criteria:**

#### **Inclusion Criteria**

- Must present with chronic back pain that can be of multifactorial etiology inclusive of axial and radicular back pain
- 18 years of age or older
- Report a Numerical Rating Scale (NRS, or Visual Analog Score VAS) score of greater than 6/10
- Must be willing to for the duration of the study make no pharmacological adjustments or have additional Interventional therapies, as reported by the patient
- Must have the cognitive capacity to provide consent/assent
- Must be able to sit up in a chair during the recording session
- Must demonstrate understanding of the protocol, its purpose and subject participation
- Headsize >54cm and <62cm in circumference in order to fit the current headset design
- Must be fluent in English

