## 9. RESEARCH DESIGN AND METHODS

This will be a single arm clinical trial with up to 25 subjects undergoing NF training in VR using the NEVR prototype and protocol. This is a feasibility study where only one arm (NF group) is needed for demonstration of feasibility; the number of subjects is based on a recently published study by Mayaud et al. 2019.

Each patient will be recruited from [name] patient population, and after signing informed consent will undergo a cognitive and behavioral pain assessment followed by 20 NF sessions, every other day or 3 times per week. Each session will take up to 1 hour and will consist of: donning of NEVR system, recording EEG while subjects sit with their Eyes Open then Eyes Closed for EEG threshold calibration, followed by performing six 5-minute blocks of NF. Subjects will then be asked to conduct a brief usability survey after each session. At the end of the 20 sessions, subjects will undergo the same cognitive and behavioral assessment conducted at the study's onset.

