## **11. RECRUITMENT AND PROCEDURES PREPARATORY TO RESEARCH**

Patients will be recruited from UCSD Pain Clinic's current patient population. The PI and Sub-investigators (listed below) will refer subjects to the study who are interested in participating in the study. The investigators associated with this study will inform the UCSD Pain Clinic physicians at one of their weekly clinic in-service meetings of this study and its eligibility requirements once this study is IRB approved. Recruitment will not be limited to the UCSD. Outside referrals will be accepted from community physicians. Subjects' participation or non-participation will in no way affect their current or future medical care.

Interested patients will be referred to [name], PhD or [name] at UCSD to be scheduled

for study visit #1, at which time the subject will be consented.

If we receive no referrals as a result of this recruitment strategy and the need for additional recruitment materials/avenues are needed, the study flyer, poster, postcards, and emails to community doctors will be submitted at a later date for review and approval by UCSD IRB prior to use.

Recruitment materials will be reviewed and approved by the IRB before they are used for the study.

For pre-screening recruitment purposes ONLY, we are requesting for a partial waiver of informed consent to interrogate the EPIC database and identify potential prospective research participants who meet the eligibility criteria for enrollment as listed in Item 10 Human Subjects.

The investigator believes the pre-screening to be used for recruitment meets the following requirements for this request per 46 CFR 46.116:

1. The (pre-screening) procedure is considered no more than minimal risk to the potential subjects, since we will not perform any procedure and the probability and magnitude of harm or discomfort anticipated in the research are not greater than those ordinarily encountered in daily life.
2. The waiver or alternation will not adversely affect the rights and welfare of the subjects.
3. The (pre-screening) research could not practicably be carried out without the waiver or alternation; and.

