## **20. COMPENSATION FOR PARTICIPATION**

\$200 total for completion of study per subject. \$10 for each visit for 20 visits, paid in \$30 increments.

Payments will be prorated for visits completed if they withdraw from the study.

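### Patients enter on a pain score above 6/10 and the uncontrolled pre/post change on that scale is read as a treatment effect, with no rule keeping the qualifying score out of the baseline

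*Combined protocol and SAP*

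**What the plan says.** Section 10, Inclusion Criteria, admits patients who "Report a Numerical Rating Scale (NRS, or Visual Analog Score VAS) score of greater than 6/10". No repeat reading, averaging or timing is described.

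Section 9, Pain Assessments, lists the NRS/VAS as an outcome, measured before and after sessions 1, 10 and 20.

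Section 9 gives the design: "This will be a single arm clinical trial with up to 25 subjects". The reason offered for one arm is that "This is a feasibility study where only one arm (NF group) is needed for demonstration of feasibility".

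Section 9, Statistical Analyses, plans "paired t-test or Wilcoxon signed-rank tests to determine the effects of the treatment", with comparisons "both across the first and last sessions and across the entire 20 sessions". Regression to the mean is not mentioned anywhere.

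Three places bear on when the scores are taken:
- Section 11 sends interested patients "for study visit #1, at which time the subject will be consented", and Section 9 places the baseline battery after consent.
- Section 20 pays "for each visit for 20 visits", the same number as there are sessions.
- Section 11 also refers to a screening visit and says eligibility may be settled during counselling, but attaches no pain score to either.

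**The concern.** Chronic back pain scores fluctuate. A patient admitted because one reading was high will, on average, give a lower reading later with no treatment at all. A control arm selected by the same rule would show the same expected fall, and it would cancel in the comparison between arms. Here there is no such arm, so the fall stays in the paired difference and the analysis section assigns it to the device.

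The problem is greatest if one reading both qualifies the patient and serves as baseline. Consent at the first visit, together with a paid-visit count equal to the session count, makes that possible, and nothing rules it out. At stake is the main clinical reading of Aim 1, which is framed as validating the system in patients: a significant fall in pain could be taken as validation when no effect exists.

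**Working it through.** **Figures in the plan.** The sample size (20 in Aim 1, up to 25 in Section 9) rests on a published precedent, with no effect size, SD, alpha or power, so there is no power calculation to reproduce. The payment section is consistent with itself: 20 visits × $10 = $200. No separate paid baseline visit appears.

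**Inputs from the documents.** Entry threshold 6; 20 patients (Aim 1); one arm; paired t-test or Wilcoxon signed-rank test.

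**Inputs assumed, because the documents give none.** Scores in the referred clinic population are normal with mean 5 to 7.5 and SD 2. The correlation r between baseline and end of treatment is 0.6 to 0.8. The test is two-sided at 5%, so a false significant fall has a nominal rate of 2.5%. There is no true effect, and the qualifying score is the baseline.

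**Expected fall.** With k = (6 − mean)/SD:

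fall = SD × (1 − r) × φ(k) / [1 − Φ(k)]

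- Mean 5, r 0.6: k = 0.5; φ/(1 − Φ) = 0.3521/0.3085 = 1.141; fall = 2 × 0.4 × 1.141 = 0.91.
- Mean 7.5, r 0.8: k = −0.75; φ/(1 − Φ) = 0.3011/0.7734 = 0.389; fall = 2 × 0.2 × 0.389 = 0.16.

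**Chance of a significant fall.** Simulated with 20,000 trials per setting, n = 20, paired t-test, scores limited to 0–10:

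| Clinic mean | Fall, r 0.6 | Significant | Fall, r 0.8 | Significant |
|---|---|---|---|---|
| 5 | 0.91 | 66% | 0.46 | 36% |
| 6 | 0.64 | 38% | 0.32 | 20% |
| 6.5 | 0.52 | 27% | 0.26 | 15% |
| 7 | 0.41 | 19% | 0.20 | 11% |
| 7.5 | 0.31 | 13% | 0.16 | 8% |

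**Sensitivity.**
- SD: at mean 6 and r 0.6 the fall is 0.48 with SD 1.5 and 0.80 with SD 2.5.
- Number of completers: the stated 10–50% drop-out leaves about 12 to 22 of 25. At mean 6, SD 2 and r 0.7, a significant fall occurs in 18% of trials with 12 completers, 29% with 20 and 37% with 25.
- Choice of test: the Wilcoxon test is at most 5 percentage points lower than the t-test.

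**If baseline is a separate reading** (n = 20, mean 6, SD 2):
- With a stable level plus independent fluctuations, the mean fall is about 0 and false significant falls occur in 2–3% of trials, in line with the nominal rate.
- If the correlation decays with time (0.7 to 0.9 from screening to baseline, 0.5 to 0.9 from baseline to end), the rate is still 8–39%.

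**The case against.** The strongest reply is that the documents never say the qualifying score is the baseline. The payment section is not a visit schedule, an unpaid screening visit is possible, and Section 11 allows eligibility to be settled at counselling. This stands: the timing is unspecified, not shown to be wrong, and the figures above are conditional on a shared reading. Against it, the items that Section 11 names for pre-screening do not include a pain score, and no rule requires a second reading.

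The inputs are also assumed. Patients come from a pain clinic whose physicians are told the entry rules, so a mean of 7 or more is plausible. The rates then drop to about 8–19%. That stands too, and is why the range extends to 7.5.

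Finally, this is a declared feasibility study with no primary endpoint, success threshold or go/no-go rule tied to a p-value. That lowers the consequence and justifies having one arm. It does not justify an uncontrolled test read as a treatment effect. The bar on medication changes limits co-intervention but does not stop a score selected for being high from falling.

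A reader might infer that every pre/post result is compromised. The documents do not support that. The bias is weaker for change within a session and for the DALLAS scale, which is not the entry measure, and it does not bear on the electrode and design work of Aim 2.

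**Conclusion.** The point holds in conditional form. Selection on a high score, the same scale as outcome, a single arm and a treatment-effect reading are all in the documents. If the qualifying reading doubles as baseline, regression to the mean alone gives an expected fall of about 0.15 to 0.9 points and a significant fall in about 8% to 66% of trials with 20 completers, against a nominal 2.5%. This rests on the assumed SD of 2, clinic mean of 5 to 7.5, correlation of 0.6 to 0.8 and two-sided 5% test. With a separate baseline and independent fluctuations the excess disappears; with a correlation that decays over time, part of it remains.

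Two stronger conclusions are tempting and not supported: that the protocol does reuse the qualifying score, and that a fall seen in this trial would be an artefact. The first is left open. The second would need a clinic mean, an SD and an untreated correlation that the documents do not give. What can be said is that the design cannot separate such a fall from a device effect, yet the analysis text reads it as one.

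**What to change.** 1. In Section 10, Inclusion Criteria, state when the qualifying score is taken and that it serves eligibility only. Take baseline from the VAS already planned before session 1, on a later day than the qualifying score, and never reuse that score. Reconcile this with Section 11, which says pre-screening information is not written down and allows research-specific screening only after consent.

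2. In Section 9, Statistical Analyses, replace the aim of determining treatment effects with that of estimating the change over treatment. Report the mean change with a confidence interval, and state that in a single arm selected on high pain this change cannot be separated from regression to the mean.

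An expected regression-to-the-mean fall should not be a required result. Entrants are selected above 6 and every planned reassessment comes after treatment has begun, so the trial cannot estimate it. If shown at all, it should be a sensitivity range under stated assumptions.

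**Cost.** Mostly wording, with no new arm or patients. If the qualifying score has to be taken after consent, a later-day baseline may need one attendance beyond the 20 now paid. The reported change may be smaller, and no efficacy claim can rest on the p-value. Because a separate baseline reduces the bias without guaranteeing its removal, the first change does not replace the second.

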#### **Exclusion Criteria:**

- Measured head size too small or too large for the EEG equipment
- Any significant skull defect
- History of a recent craniotomy (within the last six months)
- Any signs of scalp inflammation, irritation, or abnormal skin conditions
- History of epilepsy or seizures
- Known allergies to any material to be used in this project
- Sight disabilities that make participation impractical
- Hair styles with thick braids (e.g. dread locks, braids thicker than 0.5")

Due to the nature of the VR program, we cannot include subjects who cannot speak English. The program uses English instructions that is only accessible to subjects who have the headset on. As a result, we cannot use translators for this research study.

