4. Once the potential participants are identified, we will contact their PCP and ask them to distribute one of our IRB-approved flyers. If interested, study participants will contact the study team and schedule a screening visit (per IRB-approved study protocol). Whenever appropriate, the subjects will be provided with additional pertinent information after participation.

Recruitment procedures will also involve the review of subject records by designated study personnel (e.g., investigators and/or study coordinators) in order to identify potentially eligible subjects. Since Protected Health Information (PHI) will be accessed via the hospital's medical record database prior to contacting the potential subject about the research study, we are requesting a partial waiver of HIPAA authorization for access to PHI for purposes of prescreening only.

Standard HIPAA authorization to collect research data from the subject's medical record will be obtained at the time of informed consent.

A brief subset of preliminary eligibility criteria such as age, gender, and pain diagnosis in the past 12 months, will be reviewed by study personnel to determine subjects' preliminary eligibility for the research study. No written record of this information will be created. There will be no direct contact of the potential research subject by the pre-screener (i.e., study staff). The pre-screener will ask the subject's treating physician to approach the subject. The treating physician will further discuss the research study with the potential subject and ask whether they would like to be contacted by study staff to discuss the trial (i.e., counseling) and/or provide the potential subject with the study staff's contact information. Eligibility may be formally determined at the time of counseling, but any research-specific screening procedures will only be performed after informed consent is obtained and a standard, stand-alone HIPAA authorization form is signed.

For the partial waiver of individual authorization for pre-screening recruitment purposes ONLY of individual HIPPA/Protected Health Information. The following conditions apply:

1. The (pre-screening) research involves no more than minimal risk, since we will not perform any procedure and the probability and magnitude of harm or discomfort anticipated in the research are not greater than those ordinarily encountered in daily life.

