## 13. ALTERNATIVES TO STUDY PARTICIPATION

The alternative is not to participate. Subjects and their pain physician can discuss alternatives such as physical therapy, manual manipulation, regularly prescribed analgesic medications, and standard interventional therapies including steroid injection and radiofrequency ablation. The patient's decision not to participate in the study will not affect their access to standard medical care. Participation is voluntary.

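### Background pain treatment is frozen only from entry onward, so a continuing effect of a recent procedure or drug start, in either direction, would be attributed to NEVR

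*Combined protocol and SAP*

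**What the plan says.** The only rule on background pain treatment is in Section 10, Inclusion Criteria: subjects must be willing to "for the duration of the study make no pharmacological adjustments or have additional Interventional therapies", on their own report. Pain at entry is covered by "Report a Numerical Rating Scale (NRS, or Visual Analog Score VAS) score of greater than 6/10".

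On recruitment, Section 11 states: "Patients will be recruited from UCSD Pain Clinic's current patient population". It also accepts outside referrals. Pre-screening looks at "A brief subset of preliminary eligibility criteria such as age, gender, and pain diagnosis in the past 12 months". Section 13 lists what these patients and their pain physicians may otherwise consider, including prescribed analgesics and "standard interventional therapies including steroid injection and radiofrequency ablation".

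Section 9 describes a single-arm study in which consent is followed by a baseline assessment and then 20 sessions, given every other day or three times a week. Under Pain Assessments, scores are taken before and after the first, 10th and last sessions. Under Statistical Analyses, pre-post pain scores are compared by paired t-test or Wilcoxon signed-rank test, and the result is read as the effect of treatment.

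**The concern.** By freezing drugs and procedures during the study, the plan recognises that a change in other treatment would confuse the result. The freeze begins at entry, however. A change made the day before is allowed, while the same change a day later is not.

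A patient who recently had an injection, or who is held at the dose of a recently started drug, and who still scores above 6/10 meets every listed criterion. If that treatment is still taking effect, pain falls between the first and last sessions for a reason other than NEVR. If it is wearing off, pain rises and hides some of any NEVR benefit. With no control arm, nothing in the comparison separates the two sources. At stake is how the pain result is interpreted when it is carried into the Phase II decision.

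**Working it through.** **1. Is there a look-back anywhere?**

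| Place | What it covers | Reaches back over pain treatment? |
|---|---|---|
| Section 10, Inclusion Criteria | Drug changes and added procedures during the study | No |
| Section 10, Exclusion Criteria | One timed look-back: craniotomy in the preceding six months | No |
| Section 11, pre-screening | Age, gender and pain diagnosis, given as examples | Not stated |
| Section 9, design | Consent, assessment, sessions; no run-in described | No |
| Section 9, Statistical Analyses | Paired tests; no use of treatment history described | No |

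**2. Is the interval long enough?** Every other day: 19 gaps × 2 days = 38 days, and 38 / 7 = 5.4 weeks. Three per week: 20 / 3 = 6.7 weeks. The first and last scores are therefore about 5.4 to under 7 weeks apart, long enough for a recent treatment to change pain. A single session lasts up to an hour, so the before-and-after contrast within one session is little affected.

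**3. Size of the bias.** The plan gives no effect size, SD, alpha or power, so there is no figure of its own to reproduce. Let f be the share of subjects with a still-developing effect and d its remaining size in points on the 0 to 10 pain scale. Then:

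spurious mean fall = f × d

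For f = 20% and d = 2: 0.20 × 2 = 0.4 points. If other subjects have a waning effect (share g, size w), the net bias is f × d − g × w, which can be zero or negative.

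**4. Effect on the test.** Each subject's change was simulated as normal with mean 0 (no NEVR effect) and the stated SD, with d added with probability f. The statistic was t = mean / (SD / √n), referred to the two-sided 5% critical value on n − 1 degrees of freedom, with 40,000 trials per setting. The sample size n = 20 is from Section 6, Aim 1. The values of f, d and SD are assumptions.

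| f | d | f × d | Rejects, SD 2.0 | Rejects, SD 2.5 |
|---|---|---|---|---|
| 0 | – | 0 | 5.0% | 5.1% |
| 10% | 1 | 0.1 | 5.6% | 5.3% |
| 20% | 2 | 0.4 | 12.1% | 10.0% |
| 30% | 2 | 0.6 | 20.7% | 15.6% |
| 50% | 3 | 1.5 | 72.1% | 58.5% |

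In the 20%, 2-point case, rejections in NEVR's favour are 11.8% (SD 2.0) and 9.6% (SD 2.5), against 2.5% with no background effect.

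**5. Other sample sizes.** Section 10 caps enrolment at 25 and anticipates 10% to 50% drop-out. Half of 25 is 12.5, taken as 13. The same case rejects in 9.1% (SD 2.0) and 7.7% (SD 2.5) of trials at n = 13, and in 14.3% and 11.1% at n = 25.

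**6. If the gap is closed.** With f = 0 the bias from this source is zero, and the rejection rate returns to about 5% (first row of the table).

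**The case against.** A reader might infer that the gap inflates NEVR's result as a matter of course. The documents do not support that. The entry threshold keeps patients whose relief is still to come, but it equally keeps those whose treatment failed and those whose relief is fading. The direction is open.

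A reader might also count patients who are still titrating a drug as eligible. Continued titration is a series of adjustments, which the inclusion criterion already rules out. Only a recent procedure, or a recently started drug held at its dose, falls in the gap. Nor does Section 11 show that treatment history goes unseen: its pre-screening items are examples. The numbering of the instruments under Pain Assessments has gaps, so a medication record among them cannot be ruled out. Neither would amount to an eligibility rule, and the analysis section describes no use of such data. Repeated baselines spread over time might show a trend before session 1, but none are described.

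The strongest objection is proportionality. This is a small single-arm feasibility study, and closing the gap would not make its pre-post change attributable to NEVR, because placebo response and natural course remain. That stands, and it argues for a light remedy. It does not remove the point: Aim 1 is to validate NEVR in patients, the pain change is tested inferentially, and this source of confusion is cheap to record.

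**Conclusion.** The point holds as a gap in the eligibility rules and the recorded data: nothing in the documents covers pain treatment begun or changed shortly before session 1. It affects the first-to-last-session contrast, in either direction. That the gap exists is clear from the text; its size is not known. The illustrative 10% to 12% rejection rate depends on n = 20, an SD of 2 to 2.5 and a 2-point developing effect in 20% of subjects. Over shares of 10% to 50% and effects of 1 to 3 points, the range at n = 20 is about 5% to 72%, so at the low end the gap hardly matters. None of the shares, effects or SDs comes from the documents. The change is worth making because it is inexpensive, not because a large bias has been shown.

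**What to change.** - At visit 1, after consent, record the date and type of the last analgesic change and of the last interventional pain procedure. Section 11 already provides for authorization to collect data from the medical record at consent. For outside referrals, ask the patient or the referring physician. Pre-screening cannot supply this, because it creates no written record.
- In Section 9, pre-specify a sensitivity analysis that repeats the first-to-last-session pain contrast without subjects whose last change falls inside a window before session 1. The investigators should set the window before data are seen.
- Preferably, also extend the stability criterion in Section 10 back over the same window.

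The first two steps cost one added case report form field, a new collection step at visit 1 and one extra analysis on a smaller sample. The third may delay some entries, which matters in a 12-month study of at most 25 subjects. If that is unacceptable, the first two steps alone exclude nobody and still let a reader see whether the result depends on recently treated subjects.
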